8. Video instruction: <https://www.youtube.com/watch?v=hsAyURaBKv0>

Development of methods and algorithms for diet design based on gut microbiota analysis

Statistical analysis

Number of clinical trial: 1631

Project number: NSP67

Approved by Ethical Committe of National Institute for Health Development

25.10.2016

Statistical analysis

Based on sample size calculations, we estimated that with 17 participants, the study would have more than 80% power to detect a significant difference among weight loss study group, assuming a mean BMI reduction by 3 kg/m², with a mean BMI and standard deviation of 35 and 3.2 kg/m², respectively, at an alpha level of 5%.

Statistical analysis included bacteria with average colonization frequency > 70% and average abundance > 0.001. Analysis of data was carried out in R statistical programming language, version 3.5.0 (28). The resulting p-values were corrected for multiple comparisons for each phylogenetic level using Benjamini-Hochberg correction (FDR). A corrected p-value < 0.1 was considered statistically significant. Unless stated otherwise, corrected P values are shown in the text.

Pairwise comparisons were evaluated using Wilcoxon signed-rank test, for the comparison of test and reference groups Kruskal-Wallis test was applied.

To control for within-subject variability, we used the subsequent sample-pairs as within-subject controls and compared β -diversity before and after the intervention. This was also applied to reference group samples. The following cutoffs were used: *, p < 0.05; **, p < 0.01; ***, p < 0.001; ****, p < 0.0001.

Agglomerative hierarchical clustering

Ward's agglomerative hierarchical clustering on a distance matrix was generated from a species by sample Bray-Curtis distance matrix. The method produces a dendrogram by treating each sample as a singleton cluster, merging pairs of clusters until all clusters have been merged into one big cluster containing all samples. Ward's agglomeration method minimizes the total within-cluster variance.

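### Is the SAP's claim of more than 80% power with 17 participants wrong, or too vague to stand, because it names no test and does not cover the microbiota comparisons?

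*SAP*

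**What the plan says.** The sample-size paragraph of the SAP (Statistical analysis) is a single sentence. It claims that "with 17 participants, the study would have more than 80% power to detect a significant difference among weight loss study group". The effect behind this claim is a fall of 3 kg/m² in mean BMI, tested at 5% alpha. The spread is stated in the words "with a mean BMI and standard deviation of 35 and 3.2", in units of kg/m². The sentence names no test and no sidedness, and gives no SD for the change in BMI.

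The rest of the section concerns bacteria. Taxa are filtered by colonization frequency and abundance, and p-values are Benjamini-Hochberg corrected within each phylogenetic level. The decision rule is "A corrected p-value < 0.1 was considered statistically significant". Paired data go to the signed-rank test. For the other contrast the SAP says that "for the comparison of test and reference groups Kruskal-Wallis test was applied". Before/after β-diversity is compared, and "This was also applied to reference group samples". On reporting, the SAP says "Unless stated otherwise, corrected P values are shown in the text".

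Neither document gives the size of the reference group. The Protocol's General plan places faecal sampling on days 4 and 32, which is 28 days apart, and lists a weight measurement.

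**The concern.** There are two reasons for doubt.

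First, the wording does not fix the contrast. The SAP plans both paired comparisons and comparisons with a reference group, and the power sentence points to neither test. The SD of 3.2 is given next to the mean BMI of 35, so it reads as the spread of BMI between people. That is the SD a between-group comparison uses. Put into a two-sided test of 17 versus 17, it gives less than 80%, so one reading makes the SAP's only power figure false.

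Second, the calculation concerns BMI, while every analysis then described concerns the microbiota. A reader who has just met "more than 80% power" could carry it over to taxon results, to which it does not apply. If only p-values were reported, a taxon with a moderate true change would often look the same as one with no change. The stakes would be an overstated claim of power and null taxon results read as evidence of no effect.

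**Working it through.** **Inputs from the SAP:** n = 17, reduction 3 kg/m², SD 3.2 kg/m², alpha 5%. **Assumed, because the documents do not give them:** a two-sided test, the before/after correlation r, the reference-group size and the number of taxa.

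**1. Reproducing the stated figure (before/after, SD of change 3.2).** The standardised effect is 3/3.2 = 0.9375. The noncentrality is 0.9375 × √17 = 3.87 on 16 degrees of freedom, with critical value 2.120. Power is 95.2% by paired t-test and about 94% by signed-rank simulation. The claim of more than 80% holds.

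**2. Before/after, with 3.2 as the SD of BMI level.** The SD of change is 3.2 × √(2(1 − r)).

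| r | SD of change | Power (paired t) |
|---|---|---|
| 0 | 4.53 | 72.8% |
| 0.2 | 4.05 | 81.8% |
| 0.5 | 3.20 | 95.2% |
| 0.7 | 2.48 | 99.7% |

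Power is 80% at an SD of change of 4.144. The matching correlation is r = 1 − 4.144²/(2 × 3.2²) = 1 − 17.17/20.48 = 0.16. The signed-rank test needs r of about 0.22.

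**3. Between groups, SD 3.2.** For 17 versus 17 the noncentrality is 0.9375 × √(17/2) = 2.73 on 32 degrees of freedom. Power depends on the method:

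- two-sided t-test: 75.5%
- Kruskal-Wallis (simulated): about 73%
- two-sided normal approximation: 78.0%
- one-sided t-test: 84.8%

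It also depends on the unknown reference-group size. By two-sided t-test, 17 against 20 gives 78.9%, against 22 gives 80.7% and against 30 gives 85.6%. The shortfall therefore needs three choices that the SAP does not make: a between-group BMI test, a two-sided level and a reference group of about 21 or fewer.

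**4. Microbiota comparisons.** No stated figure exists to reproduce. With 17 pairs and the signed-rank test, 80% power needs a change of 0.75 SD for one uncorrected 5% test. At the strictest Benjamini-Hochberg step (0.1/m) it needs 0.87 SD for m = 5 taxa and 1.27 SD for m = 100.

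For a true change of 0.5 SD, simulation with independent taxa gives these powers per changing taxon:

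- 1 of 100 taxa changing: about 5%
- 6 of 20 taxa changing: about 24%
- all 5 of 5 taxa changing: about 50%
- a single uncorrected test: about 45%

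The tenfold spread comes entirely from the assumed number of taxa and the share that change. No single figure can be attached to the plan.

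**The case for a change.** The strongest case for a change is that the remedy is cheap and the gap is not trivial. The SD of change is the input that matters for a paired calculation, and the SAP does not give it. The study's title is about gut microbiota, yet BMI appears only in the power sentence, so the planned inference has no documented sample-size basis. One clarifying sentence, a statement of detectable effects, and estimates with intervals beside the corrected p-values would need no new data.

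The omissions stand as described, and a fuller sample-size paragraph would read better. The rest carries less weight.

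- The power sentence does identify its contrast well enough. It names a reduction, and it names the weight-loss group without mentioning the reference group. The Kruskal-Wallis test is introduced later, after the paragraph on bacteria.
- Detectable effects written into the SAP now would rest on taxon counts and a reference-group size that the documents do not contain.
- Saying that no estimates are planned infers too much from silence. The SAP says which p-values appear in the text, not that effect sizes are left out. An analyst can add them without amending the plan.
- Limited power for individual taxa is common in FDR-controlled screening and does not invalidate the tests.

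**Conclusion.** No stated figure is shown to be wrong. On the natural before/after reading, 17 participants give 95.2% power if 3.2 is the SD of change, and more than 80% if it is the SD of BMI level and the correlation exceeds about 0.16 (t-test) or 0.22 (signed-rank). The documents give no correlation. My judgement is that two BMI values in the same people weeks apart would correlate far more strongly than that. The conclusion also takes the 3 kg/m² reduction as given. It is 3/35 = 8.6% of the mean BMI, and the SAP states neither its source nor the interval over which it is expected.

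The 75.5% figure is correct arithmetic for a comparison that the SAP does not describe. What remains is missing detail: test, sidedness and SD of change for BMI, and no power basis for the taxon, β-diversity and reference-group comparisons. Supplying it would leave the tests, the FDR threshold, the number of participants and every result as they are. A careful analyst reads the power claim as applying to BMI only and does not take a non-significant taxon as evidence of no change. The plan needs no change on this point.

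### Do the 5% planning alpha, the corrected p < 0.1 rule and the stars from p < 0.05 conflict, and does correcting each phylogenetic level separately leave error uncontrolled?

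*SAP*

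**What the plan says.** Everything relevant is in the SAP, under Statistical analysis.

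- **First paragraph (sample size).** It claims that "with 17 participants, the study would have more than 80% power to detect a significant difference", "assuming a mean BMI reduction by 3 kg/m²" and a "mean BMI and standard deviation of 35 and 3.2 kg/m²", "at an alpha level of 5" per cent. This concerns BMI only, and sidedness is not given.
- **Second paragraph (bacteria).** After a filter on how often and how abundantly a bacterium occurs, it says: "The resulting p-values were corrected for multiple comparisons for each phylogenetic level using Benjamini-Hochberg correction (FDR"). The next sentence is "A corrected p-value < 0.1 was considered statistically significant". The paragraph ends by making corrected values the default for p-values reported in the text.
- **Third paragraph (tests).** Wilcoxon signed-rank is used for paired comparisons and Kruskal-Wallis for test against reference group.
- **Fourth paragraph (β-diversity).** Before and after samples are compared within subject, and the same is done for the reference group. A star legend follows, with cutoffs at 0.05, 0.01, 0.001 and 0.0001.

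The SAP does not give the number of levels, the number of taxa per level or the size of the reference group. It does not say whether the 0.1 rule extends to BMI or β-diversity, or whether the stars mark raw or corrected values.

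**The concern.** Three numbers that look like significance levels stand within a few lines of each other. The 0.1 sentence is the only one that defines significance, and it is not expressly limited to bacteria. For a single test the Benjamini-Hochberg correction changes nothing, so if the rule covered β-diversity or BMI it would amount to a 10% test. A β-diversity p-value of 0.08 would then be significant by the second paragraph and unstarred by the fourth. A BMI p-value of 0.08 would pass the 0.1 rule and fail the alpha that justified 17 participants.

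The second worry is the correction family. Phylogenetic levels are sums of the same reads, and each level gets its own 10% allowance. The 10% rate therefore need not hold over everything reported. At stake is how much trust a reader can place in a list of changed bacteria when few or none truly changed.

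**Working it through.** **1. The plan's own figure.** Inputs from the SAP: n = 17, difference 3, SD 3.2, alpha 5%. Taking 3.2 as the SD of the change and a two-sided paired test:

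- Noncentrality = (3/3.2) × √17 = 3.87.
- Normal approximation: Φ(3.87 − 1.96) = 97.2%. With the noncentral t: 95.2%.
- If 3.2 is instead the SD of BMI, the SD of the change is 3.2 × √(2(1 − ρ)). Power is 84.2% at ρ = 0.25 and 72.8% at ρ = 0.

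The claim of more than 80% is reproduced in the paired reading for ρ of about 0.25 or more. The 5% is a coherent planning alpha for one BMI comparison and says nothing about taxa.

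**2. How much the scope question matters for a single test.** With SD of change 3.2, paired-t power is 95.2% at 0.05 and 98.0% at 0.10. Under the planned effect, p falls between the two thresholds with probability 98.0 − 95.2 = 2.8%. With no effect it does so with probability 10 − 5 = 5%. The disputed zone is narrow either way.

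**3. The three thresholds side by side.**

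| Threshold | Where | Role |
|---|---|---|
| 5% | sample size paragraph | per-test alpha, BMI |
| corrected p < 0.1 | bacteria paragraph, right after the per-level correction | FDR for the taxon screen |
| stars from 0.05 | β-diversity paragraph | display marks |

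A per-test alpha and an FDR level are different quantities and need not be equal. A corrected taxon p-value between 0.05 and 0.1 has a stated verdict: significant. The absence of a star does not reverse it.

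**4. Error across levels if nothing changes.** With k independent families at 0.1, the chance of any false finding is 1 − 0.9^k. The number of levels is an assumption:

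| k | 2 | 3 | 4 | 5 | 6 | 7 |
|---|---|---|---|---|---|---|
| chance | 19% | 27% | 34% | 41% | 47% | 52% |

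Levels are nested, so independence overstates this. Simulations with 60 assumed species summed into five higher levels, 17 subjects per group and no true effect gave 28% to 33% for six levels in the diet before/after contrast, and 20% when three levels were used. One pooled family gave about 9% at 0.1 and 3% to 5% at 0.05.

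**5. Number of contrasts.** Three contrasts would give 1 − 0.9^18 = 85% under independence and about 60% to 70% in nested simulation. That count needs a before/after test of taxa in the reference group, but the SAP mentions the reference pairs only for β-diversity. With the two contrasts the text supports, treated as independent, the nested figures become 1 − 0.72² = 48% to 1 − 0.67² = 55%.

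**6. Error when something does change.** For six assumed levels of 5, 8, 10, 15, 30 and 50 taxa (118 in all) with independent tests, the FDR pooled over levels is about 0.48 if nothing changes. It is about 0.27 if only three species change, and about 0.10 if 20% of taxa change at every level (effect of 3 standard errors). Within each level it stays at 0.10.

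**7. What pooling costs.** In a level of 5 taxa, a lone finding needs raw p ≤ 0.1/5 = 0.02. In a pooled family of 118 it needs p ≤ 0.1/118 = 0.00085, and at q = 0.05 it needs p ≤ 0.05/118 = 0.00042. A genuine shift in one high-level group would be much harder to show with 17 subjects.

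**The case for a change.** The strongest case for a change is that the 0.1 sentence carries no stated limit, no primary endpoint is named for the tests, and nothing controls error across levels. Even with nesting, level-by-level correction roughly triples the chance of a false claim when nothing changes (28% against 9%). With 17 subjects and a diet period of about four weeks, few true effects cannot be ruled out. Wording and one changed call in R would settle it.

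Much of this is factually right, and the tripling stands under its assumptions. Three things weaken it as a ground for change.

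- The large figures assume that no taxon changes. The pooled rate comes down to about 10% when effects are spread over the levels.
- A comparison of 33% with 3% changes pooling and threshold together. Pooling alone gives about 9%, and the rest comes from a stricter q. Nothing in the documents requires the FDR level to equal the BMI alpha.
- Pooling nested levels is not clearly better. One changed species also moves its genus and family, so the same signal is counted repeatedly. Per-level FDR matches a list of taxa reported level by level.

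To say that the study would usually report a false bacterium goes too far: one contrast gives a minority of cases, and two give about half, only under the extreme null.

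**Conclusion.** No change is called for. The thresholds do not conflict once each is read in its own paragraph, and corrected taxon p-values between 0.05 and 0.1 have a clear verdict. Two gaps remain: whether 0.1 reaches BMI and β-diversity, and whether the stars mark corrected values. Both are missing detail that an analyst would fill in the obvious way, with 0.05 for single tests and FDR 0.1 for taxa. The default of reporting corrected values already answers part of the second.

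The per-level family is a disclosed choice with a known price. FDR is held at 10% within a level, and under a complete null the chance of at least one false taxon in one contrast is about 20% to 33%, against about 9% if pooled at 0.1. Those figures rest on assumed numbers of levels and taxa and on 17 subjects per group, since the SAP gives neither taxon counts nor the reference-group size. A stricter family or a lower q would buy fewer false taxa at the cost of missed true ones, which is a fair trade-off to leave where it is. A reader should simply take the 10% as applying to each level, not to the whole set of reported bacteria.

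### The SAP does not say how signed-rank p-values are computed when paired differences are zero or tied; R's usual fallback is conservative in the tail that the FDR step uses and can hide isolated taxon changes

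*SAP*

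**What the plan says.** The SAP's section on statistical analysis fixes four things that bear on this point:

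- Test: "Pairwise comparisons were evaluated using Wilcoxon signed-rank test".
- Software: "Analysis of data was carried out in R statistical programming language, version 3.5.0".
- Taxa tested: "Statistical analysis included bacteria with average colonization frequency > 70% and average abundance > 0.001".
- Decision rule: Benjamini-Hochberg within each phylogenetic level, then "A corrected p-value < 0.1 was considered statistically significant".

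The protocol's general plan gives one before/after pair per participant, with faecal samples on days 4 and 32. The only participant number is in the SAP's sample-size sentence, which concerns BMI: "with 17 participants, the study would have more than 80% power".

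Neither document names an R function or package, an exact or permutation option, a rule for zeros or ties, a transformation of the abundances, or the number of taxa per level.

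**The concern.** A taxon can pass the filter while absent from nearly 30% of samples. If a participant lacks it on both days, the paired difference on the raw abundance scale is zero. Base R's signed-rank function then drops the zero and abandons the exact null distribution for a continuity-corrected normal approximation. A tie among the non-zero differences has the same effect.

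At an uncorrected 5% cut-off this hardly matters. Benjamini-Hochberg, however, works with much smaller p-values when many taxa are tested and few have changed. With 12 to 16 informative pairs the approximation is too large in that region.

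Two things follow. Incompletely carried taxa, which the filter deliberately retains, lose power. And exact p-values (taxa without zeros or ties) are ranked together with inflated ones in a single FDR step. A finding of no change for a taxon could then reflect the approximation and not the data. In a project that designs diets from microbiota data, that is worth avoiding.

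**Working it through.** **The plan's own figure.** The stated power concerns BMI. Inputs from the SAP: "assuming a mean BMI reduction by 3 kg/m²", "with a mean BMI and standard deviation of 35 and 3.2 kg/m²", "at an alpha level of 5"%. Taking 3.2 as the SD of the change, the noncentrality is (3/3.2) × √17 = 3.87 on 16 df, and a two-sided paired t-test has 95.2% power, so the claim of more than 80% holds on that reading. This point does not touch it.

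**How many pairs can be zero.** Assume 17 analysed participants (the BMI planning number) and carriage averaged over their 34 samples. More than 70% of 34 means present in at least 24 and absent from at most 10. If absences coincide, that is 10/2 = 5 double-absent participants, leaving 17 − 5 = 12 informative pairs.

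**How often a zero occurs.** Chance of at least one double-absent pair among 17:

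- 75% carriage, absences independent across days: 1 − (1 − 0.25²)^17 = 67%; more if absences persist.
- 90% carriage, independent: 1 − (1 − 0.10²)^17 = 16%.
- 90% carriage, fully persistent: 1 − 0.90^17 = 83%.

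**What R does.** Checked in R 4.3.3; that 3.5.0 behaves alike is an assumption. Seventeen distinct positive differences give the exact p of 0.0000153. With one zero pair the paired test warns that no exact p can be computed and returns 0.00048; with three, 0.0011; with five, 0.0025. Setting exact=TRUE does not change this.

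**Smallest attainable two-sided p.** With n informative pairs all changing in the same direction:

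- Exact: 2/2^n.
- Approximation: z = [n(n+1)/4 − 0.5] / √[n(n+1)(2n+1)/24], p = 2Φ(−z).

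For n = 12: exact 2/4096 = 0.00049; z = (39 − 0.5)/√162.5 = 3.02, p = 0.0025.

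A lone changed taxon ranked first among m taxa has corrected p of m × p if no other taxon helps it, so it passes when m × p < 0.1. For n = 12: 0.002526 × 39 = 0.0985 passes and × 40 = 0.101 fails; 0.000488 × 204 = 0.0996 passes.

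| Informative pairs | Zero pairs of 17 | Exact p | Fallback p | Largest m, exact | Largest m, fallback |
|---|---|---|---|---|---|
| 16 | 1 | 0.000031 | 0.00048 | 3276 | 207 |
| 14 | 3 | 0.00012 | 0.0011 | 819 | 91 |
| 13 | 4 | 0.00024 | 0.0017 | 409 | 60 |
| 12 | 5 | 0.00049 | 0.0025 | 204 | 39 |

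**Where the two versions part.** Largest rejecting value of the smaller rank sum, exact against fallback:

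- 12 pairs: 13 and 13 at p ≤ 0.05; 7 and 5 at 0.01; 1 and unattainable at 0.001.
- 14 pairs: 21 and 20 at p ≤ 0.05; 12 and 10 at 0.01; 4 and unattainable at 0.001.

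**Power after Benjamini-Hochberg at 0.1.** Simulated with 17 participants, normal differences and a shift of 1.2 SD of the paired difference. Carriage is uniform on 70-100% and 80% of absences persist unless noted. None of these values comes from the documents except the 70% floor and the 17.

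| Scenario | Exact | Fallback | Loss (points) |
|---|---|---|---|
| 60 taxa, 1 changed | 68% | 48% | 20 |
| 60 taxa, 1 changed, 40% persistence | 75% | 62% | 13 |
| 60 taxa, 1 changed, carriage 90-100% | 81% | 71% | 10 |
| 60 taxa, 1 changed, carriage 90-100%, 40% persistence | 81% | 77% | 4 |
| 60 taxa, 3 changed | 80% | 70% | 10 |
| 60 taxa, 10 changed | 93% | 91% | 2 |
| 30 taxa, 1 changed | 76% | 63% | 13 |
| 20 taxa, 2 changed | 89% | 86% | 3 |
| 10 taxa, 1 changed | 87% | 85% | 2 |

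Simulation error is a few points in the one-changed cells; repeated runs of the first row gave 66-70% against 47-49%. Realised FDR stayed below 0.1 with both versions.

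**The case against.** The strongest reply is that the SAP names a test, not a function. A function's default is not a planned choice, and the analysts may already use exact p-values or transform abundances so that a double absence no longer gives an exact zero. That stands: the documents show an unspecified option, not a demonstrated error. It does not dispose of the point, because the fallback is what the named test most naturally produces in the named software, and asking the base function for an exact p does not avoid it.

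The size is also conditional. The 20-point loss needs many taxa at a level, one true change and persistent absences. The abundance filter may favour well-carried taxa, and correction is by phylogenetic level, so levels with few taxa lose little. This too stands, and is why a range is given.

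Four stronger readings are tempting, and the documents do not support them:

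- That taxa present in every participant are affected. With 17 non-zero, untied differences R returns the exact p; only ties would trigger the fallback.
- That reported changes become less trustworthy. The fallback is conservative, so the risk is missed changes, not extra false discoveries.
- That the Kruskal-Wallis comparison with the reference group needs permutation p-values as well. The size of that group is not given, and no calculation here bears on it.
- That the BMI sample size is undermined. It is a separate calculation.

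Finally, the SAP is written in the past tense. If results exist, moving to a more powerful p-value is a post hoc change and has to be called one.

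**Conclusion.** The point holds as a conditional loss of power that costs almost nothing to remove. It rests on base R's default function, on double absences giving exactly zero differences, on about 17 analysed pairs and on two-sided tests.

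Under those assumptions, once three to five participants lack a taxon on both days, a lone and perfectly consistent change cannot be declared at levels with more than 91, 60 or 39 taxa (three, four or five such participants), although exact p-values would allow 819, 409 or 204. In the scenarios above the average loss is about 2 points when many taxa change, about 2 to 5 when few are tested or when carriage is high and absences seldom persist, and about 20 with 60 taxa and one changed. Error control is intact under either version. The plan should be changed, but nothing in it is shown to be invalid.

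**What to change.** Add one sentence to the SAP paragraph on tests:

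> All signed-rank p-values are computed from the exact sign-flip (permutation) distribution of the non-zero pairs, with mid-ranks for ties; Benjamini-Hochberg is applied to these p-values.

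This needs a function other than base R's default, since the exact option there is overridden by zeros. Computation is trivial: 17 pairs give at most 2^17 = 131,072 sign patterns. No new data are needed, and the test keeps its nominal level. If exact p-values are already in use, the sentence records that and no result changes. If results from the fallback already exist, label the exact rerun as a post hoc change.
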